#### 6.6.2 Who provides the intervention?

The intervention is provided by The University of Sydney speech pathology students under the supervision of the speech pathologists in the research team. The students will be trained by the chief investigator in the treatment and data collection before the commencement of the intervention block. Supervision is provided throughout the intervention block and in accordance with Speech Pathology Australia and The University of Sydney speech pathology supervision guidelines.

## **6.7 Participant Withdrawal**

Participants will be informed in the Participant Information Statement about their right to withdraw at any time. If the participant wishes to withdraw, they are asked to inform one of the research team. At this point, participants will be asked if they wish for the researchers to retain or destroy already collected research data. If the participant agrees, then their data will be retained and analysed using intention to treat analysis. If the participant does not agree, then their data will be destroyed. Participants who decide to withdraw from the research will be asked for their reasons and these will be recorded and reported if they are provided and if consent is provided.

As the participation is also a student clinical placement, participants who wish to withdraw from the research may continue to receive the treatment if they wish but the research data will not be collected.

### **6.7.1 Handling of withdrawals and losses to follow-up**

Intention to Treat (ITT) will be used to statistically analyse the results if there is loss to follow up, or if there are any deviations from the original assigned groups.

### **6.7.2 Participant Replacement following withdrawal**

Replacements will not be sought for participants who withdraw from the study, as attrition has been accounted for in our sample size.

## **6.8 Expected Duration of Study**

The expected study duration is 21 months. Subject to ethics approval we anticipate recruitment of participants to commence in March 2024. The last participant will finish no later than December 2025.

## **6.9 Ethics Approval**

Ethics approval will be sought from the University of Sydney Human Research Ethics committee.

## **6.10 Modifications to the Protocol**

Any modifications to this application will be submitted to the HREC and CTSO before they are implemented and will be recorded in the clinical trials register (ANZCTR)

## **6.11 Protocol Violations**

To minimise and prevent protocol violation, the following will occur:

The written treatment procedural manual will include instructions on the delivery of ReST, data recording, and data storage.

Provision of adequate training of speech pathology students on the delivery of ReST. Regular and on-going supervision of the students and observation of their treatment sessions.

Procedure for recording treatment dosage and participant responses at each session. Procedure for recording participant behavior and engagement after each session.

Procedure for logging all data recording and storing.

If a protocol violation occurs, the person responsible will inform the Chief Investigator (CI) or, in case of a student, their student supervisor within 24 hours. The CI or the student supervisor records the violation in the protocol violation form. A plan to rectify the violation will be decided between the person responsible for the violation, their supervisor where relevant, and the CI. This is also recorded in the protocol violation form.

### **6.12 Participant reimbursement**

There are no participant reimbursement or incentives.

### **6.13 Continuation of therapy**

Provided that no adverse/serious events occur the trial will continue until either of the following has been met: (i) a sufficient number of participants have been recruited, or (ii) the study period has ended.

### **6.14 Statistical analyses**

Data analysis will utilize repeated measures visual analysis. When a treatment effect is evident visually, statistical analysis within participant, across treatment phase (I.e. baseline, treatment, follow-up) will be calculated using Helmert Planned orthogonal contrasts.

Effect sizes within participant will be calculated using  $d^2$ , as this measure is appropriate for single case data (Beeson & Robey, 2006).

If there is any attrition, an intention-to-treat analysis will be conducted.

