### **4. AIMS / OBJECTIVES / HYPOTHESES**

#### Aim:

The study aims to investigate if Rapid Syllable Transition Treatment (ReST) is effective in improving speech intelligibility in adults with apraxia of speech.

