**PROCEDURES**

1. Following consent, participants will be assessed by a qualified speech pathologist (one of the investigators) using standard speech pathology tools. This assessment will take no more than one hour. Tasks will include saying words and sentences, reading a passage, having a hearing screening and completing an oral movement assessment (OMA) which includes tasks such as stick out your tongue; lick your lips, alternate between a kiss and a smile and say /a/ for as long as you can (forms attached). The assessment will be audio and video recorded.
2. Following standard ReST protocol, one of the investigators will then create a list of words for each participant consisting of 20 treatment words, 10 control (untreated) words, 10 untreated generalisation sentences and 30 generalisation words. This list of 70 items is called the Probe list and participants will be asked to say it on a number of occasions described below.

3. Prior to treatment, each participant will be asked to say the 70 item probe list on five separate days (max 30 minutes per session) and these will be recorded as the baseline performance.
4. Treatment will be provided by a trained speech pathology student for one hour twice per week for six weeks at a mutually convenient time. Treatment consists of learning to say the nonsense words. No home practice is required. Treatment may be face-to-face in the on-campus speech pathology clinic or it may be on Zoom. This choice will be up to participant preference.
5. Immediately prior to the fifth and ninth sessions, participants will be asked to say the 70 word probe list and this will be recorded. 20 minutes on each occasion.
6. Immediately following the final (twelfth) session, participants will be asked to say the 70 word probe list and this will be recorded. 20 minutes.
7. Participants will return to the clinic one day, one week, two weeks and four weeks after finishing treatment and say the 70 word probe list on each occasion. On the one week and two week post treatment occasions, they will be asked to say the list twice. Each visit will take approximately 30-40 minutes.
8. Four weeks after completion of the treatment, participants will also repeat several of the tasks completed in the initial assessment (step 1) and say the probe list for the final time (60 minutes total)
9. Following the four week appointment a short report on their individual performance in treatment will be sent to each participant for their own records.

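### The Helmert contrasts are run only where an effect is already visible in the same data, so the contrast p-values and estimates that get reported are selected on outcome

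*Protocol*

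**What the plan says.** Section 6.14 sets out the analysis in three steps.

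- Visual analysis comes first: "Data analysis will utilize repeated measures visual analysis".
- The contrasts are conditional on its result: "When a treatment effect is evident visually, statistical analysis within participant, across treatment phase" (baseline, treatment, follow-up) "will be calculated using Helmert Planned orthogonal contrasts".
- Effect sizes follow in a separate sentence with no visual condition: "Effect sizes within participant will be calculated using" d2.

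The section gives no criterion for a visible effect and no test for a series without one. Section 6.4.5 blinds those who score and transcribe the recordings but says nothing about who judges the graphs. The aim in Section 4 is to find out whether the treatment is "effective in improving speech intelligibility in adults with apraxia of speech". Sections 3.2 and 6.3 say the results will supply data for the sample size of a larger study.

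**The concern.** Whether a contrast is computed depends on the outcome that the contrast then tests. A series that rises by chance is tested; one that stays flat or falls by chance is not. Two things follow for the tests that appear in a report. Their p-values no longer have the stated frequency under no effect, because the reader sees only series already picked for rising. Their contrast estimates are averages over favourable draws and so lie too high. Calling the contrasts planned does not help when the decision to run them is taken after seeing the data.

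This is a rule that the protocol states, not a detail left to a later document. An analysis plan that follows it inherits the selection, and one that tests every series contradicts it. With six participants, leaving the contrast out for those judged not to respond changes how the set of tests reads.

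**Working it through.** **No figure to reproduce.** The protocol states no alpha, power, effect size or p-value threshold. The check is therefore what the rule does under stated assumptions.

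**Inputs from the Procedures (Section 6.2).**
- Baseline, 5 probes: "each participant will be asked to say the 70 item probe list on five separate days".
- Treatment, 3 probes: "Immediately prior to the fifth and ninth sessions, participants will be asked to say the 70 word probe list" gives 2, and "Immediately following the final (twelfth) session, participants will be asked to say the 70 word probe list" gives 1. Counting the last one as treatment phase is an assumption.
- Follow-up: 1 (one day) + 2 (one week) + 2 (two weeks) + 1 (four weeks) = 6.

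**Other assumptions.** Independent normal errors with SD 1, two-sided 0.05, the same shift in treatment and follow-up, and several versions of a visible effect.

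**Contrast.** The first Helmert contrast is −1 × baseline mean + ½ × treatment mean + ½ × follow-up mean. Its variance is 1/5 + 0.25/3 + 0.25/6 = 0.325, so SE = 0.570 SD. The pooled error has 14 − 3 = 11 df.

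**Simulated results (at least 200,000 series per scenario).** Rise means the contrast estimate.

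| Assumed visual condition | Tested, no effect | p<0.05 among tested, no effect | Tested and p<0.05, no effect | Mean contrast reported, true 0.5 SD |
|---|---|---|---|---|
| None (all tested) | 100% | 5.0% | 5.0% | 0.50 |
| Rise above 0 | 50% | 5% | 2.5% | 0.69 |
| Rise above 0.5 SD of the 5 baseline points | 21% | 12% | 2.5% | 0.92 |
| Follow-up mean above highest baseline point | 6.3% | 24% | 1.5% | 1.04 |
| Rise above 1 SD of the 5 baseline points | 7.7% | 31% | 2.4% | 1.12 |
| At least 2/3 of later points above highest baseline point | 2.8% | 46% | 1.3% | 1.22 |
| Rise above 1 pooled within-phase SD | 5.3% | 47% | 2.5% | 1.23 |
| Rise above 1 true SD | 4.0% | 49% | 2% | 1.31 |

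**Check of the estimates by formula.** For a true shift δ and a condition that the rise exceeds k, the mean reported contrast is δ + SE × φ(a)/(1 − Φ(a)), with a = (k − δ)/SE.
- δ = 0.5, k = 0: a = −0.877; 0.5 + 0.570 × 0.2716/0.8098 = 0.69.
- δ = 0.5, k = 1: a = 0.877; 0.5 + 0.570 × 0.2716/0.1902 = 1.31.
- δ = 2, k = 1: a = −1.754; 2 + 0.570 × 0.0857/0.9603 = 2.05, an inflation of 2.5%. With the SD of the five baseline points as yardstick the simulated mean is 2.06, or 3%.

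**Series left untested.** With the 1 baseline SD condition and a true shift of 0.5 SD, about 74% of series get no contrast although the effect is real.

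**Autocorrelation.** With an assumed first-order autocorrelation of 0.3, rejection under no effect is 13.0% when every series is tested and 13.0% to 62.9% among tested series under the conditions tried. The 13.0% is a separate weakness of the t-test that removing the visual condition would not cure.

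**The case against.** Visual analysis first is normal practice in a single-case design, and that part of the plan is sound. The fault lies only in making the test depend on the visual result. Four further points stand, and they limit what can be concluded.

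- **Error rate.** A reader might infer that the rule inflates false positives. It does not. The chance under no effect of both passing the visual condition and reaching p<0.05 is at most about 2.5% per series with independent errors, against 5.0% when all are tested. Read as a rule needing both, it is conservative. The p-values fail only conditionally on having been tested.
- **Estimates for non-responders.** A reader might infer that participants without a visible effect get no estimate, and that an inflated effect is carried into the larger study. The text does not support this. The d2 sentence has no visual condition, so every participant gets an effect size as well as the visual result. Sections 3.2 and 6.3 do not say which statistic would feed the later sample size.
- **Primary outcome.** A reader might infer that the primary answer is biased. The 5/3/6 series is the probe list, from which Section 6.5 derives phoneme accuracy, a secondary outcome. The primary measure is a standard score on the Assessment of Intelligibility in Dysarthric Speech. That test is listed in the pre-treatment assessment (Section 6.4.4), and several of the initial tasks are repeated at four weeks. The simulation says nothing direct about it.
- **Dependence on assumptions.** The protocol defines no visual criterion. A direction-only condition leaves conditional rejection near 5%, and large effects are barely inflated.

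None of this removes the selection in the reported contrasts.

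**Conclusion.** The point holds for the Helmert contrasts. Those reported are selected on the data they test: their p-values lack nominal meaning given selection, their estimates are biased upward, and flat or worsening series receive no test. Without the visual condition, rejection under no effect is 5.0% and a true 0.5 SD shift is estimated at 0.50 SD. With it, conditional rejection is about 5% to 49%, and the same shift is reported as about 0.7 to 1.3 SD. These ranges are illustrative: they rest on assumed visual criteria, an assumed two-sided 0.05, independent errors and the 5/3/6 probe count. d2 would be affected only if it too were reported selectively. This is a should-fix in a six-participant study with no power claim, where visual analysis leads and the effect size is unconditional.

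**What to change.** Replace the conditional sentence in Section 6.14 with: *Visual analysis, the planned Helmert contrasts (with estimates and confidence intervals) and d2 will be computed and reported for every participant and every probe item set, whatever the visual analysis shows.* It would also help to state what counts as a visible effect and who judges the graphs, since both results will then stand side by side.

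The cost is one sentence and a few more lines of output; no new data are needed. The downside is more tests. One contrast for each of six participants at an assumed 0.05, with no true effect, gives a 1 − 0.95^6 = 26.5% chance of at least one false positive, and further item sets add to that. The number of tests should be stated wherever they are interpreted. The change should be made before any series is graphed.

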## **7. ETHICAL CONSIDERATIONS (see data, section 10 for privacy and confidentiality)**

### **7.1 Potential Risks and Proposed Benefits**

#### **7.1.1 Potential Risks**

This is a relatively low-risk project and does not pose significant foreseeable risks to the participants. The speech pathology involvement is not different from the usual speech pathology practice but may involve mild distress from time to time as tasks may be difficult for the participant.

As this is a trial study of ReST with adults, there is a risk of no improvement in speech intelligibility at the end of the study. The participants are informed of this at recruitment.

Participants will receive treatment from speech pathology students. There is a small risk that the students' inexperience may impact on the intervention quality or the ability to recognise subtle signs of participant fatigue, however previous ReST studies involved speech pathology students successfully in the treatment delivery, including McCabe, et. al (2023), Murray, et. al. (2015) and Thomas et al., (2023) studies. Students will be supervised by the research team members who are experienced clinical supervisors and speech pathologists and will receive guidance and support to maintain a high standard of service delivery and participant care.

Privacy and confidentiality pose a risk. This is covered in Section 9 Data Management.

#### **7.1.2. Participant Benefits**

The participants will receive therapy and an individualised report. Attending therapy may in itself have a therapeutic effect due to positive communication interactions with the student clinicians.

### **7.2 Responsibility for liability of injury**

The participants may experience fatigue and frustration during assessments or treatment. The supervising speech pathologists and the speech pathology students will be instructed to note signs of fatigue or frustration and to give the person a short break if these occur.

The students are covered by University of Sydney insurance for clinical placements. The WHS requirements for risk minimization will be adhered to throughout the study intervention. The university will be the sponsor of the study and the FMH Clinical Governance Committee has accepted oversight.

### **7.3 Recruitment**

Recruitment will take place online (social media, email) of people from the community and to those in the University of Sydney Speech Pathology clinic patient list (by an independent clinical team member). Potential participants will be directed to contact the chief investigator or to visit the ReST website. Neither the research team or the student speech pathologists will approach or contact the potential participants prior to consent.

#### **7.3.1. Dual or unequal relationship, potential for coercion or inducement**

The participants are protected against potential coercion in that they will not be approached directly by any of the research team members.

Participants will also be informed that if they decline to participate or withdraw from the study, this will not affect their relationship with the research team or the University of Sydney.

### **7.4 Informed Consent**

The participants will be informed about the study and given the PCF and the PIS. The participant can choose whether they want to sign the consent form. If the participant declines to participate in the study, they are assured that this will not impact their relationship with the research team members, The University of Sydney and its staff.

The participant is provided the name and contact details of the chief investigator if they require further information. They are also provided the contact details of the University of Sydney Ethics committee if they have any concerns or complaints about the study.

The participants will be informed that their participation is completely voluntary. They are free to decline to attend the study, and also free to withdraw from the study at any time. This will have no implications on their relationship with the research team or the University of Sydney.

### **7.5 Clinical governance**

The clinical governance for the project is provided by the Faculty of Medicine and Health Clinical Governance committee. The protocol has been added to the Speech Pathology Model of Care (26th October 2023).

## **8. SAFETY CONSIDERATIONS**

### **8.1 Assessment and Documentation of Adverse Events**

To ensure consistent procedures and safety of the participants, the participants' progress and participation will be monitored. Speech pathologists in the research team will supervise the speech pathology students who deliver the treatment. This includes monitoring the maintenance of accurate delivery of ReST treatment and to ensure the participants' experiences during the treatments are positive. The supervising speech pathologist provides feedback and support to the students during and after the treatment sessions. Adherence to the treatment protocol and participants' experiences are discussed and adjustments are implemented where required.

Participants who become distressed will be provided with a break, with encouragement, and with appropriate support. If the participant consents to continuing, the session will recommence after a short break. Otherwise, the session will be discontinued and the discontinuation will be noted.

One of the investigators will be present whenever students are providing therapy. Direct observation of the students occurs during the first four sessions of the treatment block. After this, the frequency of direct observation will be reduced to once a week, in line with usual educational

and clinical practice. All sessions will be recorded and the student and the supervisor will review any sessions where the supervisor was indirectly supervising.

### **8.2 Adverse event reporting**

All adverse events will be reported to the chief investigator and recorded. The procedures for reporting serious adverse incidents within 72 hours will be followed.

Standard procedures for completing and submitting HREC adverse event templates and contacting the HREC office directly with urgent issues will be followed.

The data collection procedures will be monitored to ensure the accuracy of the data. Data collection monitoring includes monitoring of the consistency of data analysis, quality of video recordings, and the timeframes for uploading videos to the data storage after each therapy or assessment session. The supervisors check the data collection procedures weekly for the students they supervise. Data collection procedures are discussed at supervision meetings and adjustments are implemented where required.

## **9. DATA MANAGEMENT**

### **9.1 Data collection and storage**

Research data, including video recordings and assessment results are collected in electronic form. Any paper documents will be scanned, uploaded and the paper version deleted within two weeks of collection. Identification codes replace names in all files.

All assessment and treatment sessions are videoed, which will then be uploaded by the treating student therapist to The University of Sydney provided, password protected Sharedrive immediately after the session.

Paper copies of assessment forms are scanned and collected in electronic form. Paper copies of intelligibility ratings are scanned and collected in electronic form. The paper forms are shredded immediately after scanning.

Contact details and identifying codes will be held in a password protected encrypted file in the RDS.

Once the data is no longer being actively used it will be deleted from Sharedrive and only retained in the RDS.

### **9.3 Data retention and archiving process**

Data will be stored for 15 years which is the standard required for clinical trials. At the end of this time the project materials will be permanently deleted from the RDS.

## **10. FINANCIAL**

This study is not externally funded.

## **11. PUBLICATION POLICY / DISSEMINATION OF RESULTS**

This work will be reported in one or more journal articles and conference papers. A public summary will be published on the ReST website.

Authorship will follow the Contributor Roles Taxonomy (Credit). [name] will be 1st author unless otherwise agreed, other authors will be determined by the nature and extent of their contributions to the papers. An honours student may be added to the project and in this case, authorship will be re-

negotiated.

